## 11. Primary Endpoint (ITT, ITT age subgroups, ITT pediatric formulation subgroups, ITT virology subgroups)

Table to show the completeness of the primary endpoint should include number (%) with [14.2.2]:

- Complete data (Day of hospitalization and discharge or death)
- Incomplete data (missing day of hospitalization or discharge/death)

The following table and figure provide descriptive statistics of the primary endpoint. The table and figures should impute values of 28 days for patients who died and should censor patients with missing discharge date at the time of last follow up.

- Figure: Kaplan-Meier plot of time to hospital discharge/death (only ITT and ITT age subgroups)
- Table: with the following estimates from the Kaplan-Meier curves- 25th, 50th and 75th percentile along with min and max values in hours [14.2.3.1.x]

- The between group difference in median time to discharge will be used to estimate the treatment effect and will be reported along with a 95% two-sided confidence interval.
- Additionally, data from median, min, max converted to “days, hours”
- The p-value for the 2 group comparison of the primary endpoint analysis will be performed using the Shaw-Fay method as described in appendix 1.
- Sensitivity analyzes to exam effect of missing death or discharge data. (only ITT and ITT age subgroups)
  - Figure with Kaplan-Meier curves and Shaw-Fay p-values on the ITT only where missing death or discharge dates are imputed in the placebo group as censored at the time of last follow up and in the experimental group are imputed as events at day 28.
  - Figure with Kaplan-Meier curves and Shaw-Fay p-values on the ITT only where missing death or discharge dates are imputed in both groups as events at day 28.
  - For any imbalance seen in baseline characteristics ( $p < .05$ ) perform a cox proportional hazards model with deaths receiving event times of 28 days. Missing discharge dates will be censored at last follow up time.

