9.1 General Considerations

This is a double-blind, randomized, placebo, controlled trial in patients with hospitalized influenza-like-illness to evaluate the efficacy of NTZ compared to placebo on the time to hospital discharge. The primary analysis will use the Shaw-Fay formulation of the 2 sample Mann-Whitney-Wilcoxon rank-sum statistic. The primary endpoint will be time to hospital discharge, censored at 28 days. Patients who withdraw consent will be counted as being censored at the time of withdrawal. Patients who die by Day 28 will receive the worst ranks, (i.e., worse than any patients who remain hospitalized). Furthermore, patients who die earlier will receive worse ranks than those who die later. Patients who withdraw consent prior to day 28 are thus censored for death and discharge at the time of withdrawal. Such censoring is addressed by the method of Shaw and Fay (2013). A permutation method will be used to determine statistical significance. The primary analysis will follow the intent-to-treat principle where all randomized patients will be used in the analysis. The primary analysis will use a two-sided alpha level of .05.

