1.50 Days	1.83	.66	1.52	.78	80%	174
1.50 Days			1.52	.78	90%	232
1.25 Days	1.83	.66	1.58	.76	80%	258
1.25 Days			1.58	.76	90%	344
1.00 Day	1.83	.66	1.64	.74	80%	430
1.00 Day			1.64	.74	90%	576

^a Delta is the assumed reduction in the mean number of days in the hospital under treatment compared to placebo.

^b N is the total sample size.

We see that with about 258 patients total the study is 80% powered to detect a 1.25 day improvement in the time to hospital discharge. This difference is similar to our assumptions. To allow for up to 10% dropouts we will recruit 290 patients. If the difference was 1.5 days, the study would have 90% power to detect the difference in the treatment arms.

While a 1.25 day improvement is clinically meaningful and easily interpretable for a population with a mean hospital stay of 7.7 days, it is also a reasonable estimate of the effect of NTZ we might see. The NTZ IB describes a Phase 2b-3 study in adults and adolescents with acute uncomplicated ILI. In all subjects, the mean time to resolution of symptoms was 95 hours in the NTZ group compared to 108 hours in the placebo group, thus there is about a 12% reduction in the time to resolution (12% = (108 hr - 95 hr)/108 hr x 100%). Our hoped for treatment effect of a 1.25 day reduction in hospital duration is a 16% reduction in the time to hospital discharge (16% = (1 day/7.7 day x 100%)).

Kaplan Meier curves of time to hospitalization discharge over 28 days will be used to compare the 2 groups. In these curves, deaths will be counted as being in the hospital at day 28. The between group difference in median time to discharge will be used to estimate the treatment effect and will be reported along with a 95% two-sided confidence interval.

Important additional analyses will be to repeat the primary analysis for those who are influenza positive. Other subgroups include age (<12 years of age, \geq 12 years of age) and pathogen type.

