- Evaluate the virologic efficacy of NTZ + SOC vs. PCB + SOC with regards to:  
Restricted to those with virus detectable on Day 0
  - Table N (%) of subjects that had any virus detectable on Day 0, and no longer had any virus detectable on Day 3 [14.2.11]
    - If more than one virus was present on Day 0, both viruses must be cleared to be considered as no detectable virus. If Day 3 has a virus that was not detected on Day 0 (day 0 had virus A and Day 3 virus B), this is not considered as having no detectable virus.
    - P-value obtained using test of proportions
  - Table N (%) of subjects that had virus detectable on Day 0, and had a different virus detectable on Day 3.

## Appendix 1

The primary endpoint is time to hospital discharge or death within 28 days. The primary analysis will follow the intent to treat principal where all patients randomized will be used in the analysis and analyzed according to treatment assignment. Observations will be censored at 28 days if discharge or death does not occur before 28 days.

The Shaw-Fay methodology uses ranks to form the test statistic. The following ranking system will be followed if no loss to follow up occurs. Patients who die will be given worse ranks than those who are alive. Among those who die, early deaths receive worse ranks than those who are alive and among those alive the order of ranking from worst to best is no discharge, late, than early discharge. Table 1 gives an example of rankings for an invented data set.

Table 1. Example of rankings for invented data set. C indicates censored at day 28 or censored due to death. Larger ranks are worse than smaller ranks.

Person	Day of discharge	Day of Death	Rank
1	C	5	8
2	C	10	7
3	3	15	6
4	C	C	5
5	15	C	4
6	5	C	3

7	2	C	1.5
8	2	C	1.5

The test statistics is the sum of the ranks for patients in the Nitazoxanide group. Treatment labels will be permuted to calculate the probability of obtaining a test statistic as extreme as the observed sum of the ranks of the experimental group.

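### The primary test uses ranks with deaths worst, but the only effect estimate planned for every primary comparison is a difference in medians, a different and less precise quantity; add an estimate on the rank scale beside it

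*SAP*

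**What the plan says.** **The test.** Protocol 9.1: "The primary analysis will use the Shaw-Fay formulation of the 2 sample Mann-Whitney-Wilcoxon rank-sum statistic". On deaths it adds: "Patients who die by Day 28 will receive the worst ranks, (i.e., worse than any patients who remain hospitalized", and earlier deaths rank worse than later ones. It also fixes the level: "The primary analysis will use a two-sided alpha level of .05". SAP section 11 agrees: "The p-value for the 2 group comparison of the primary endpoint analysis will be performed using the Shaw-Fay method as described in appendix 1". SAP Appendix 1 gives the full order from worst to best (early death, late death, not discharged, late discharge, early discharge) and says: "The test statistics is the sum of the ranks for patients in the Nitazoxanide group". Significance comes from permuting the treatment labels.

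**The estimate.** SAP section 11 and protocol 9.2 both say: "The between group difference in median time to discharge will be used to estimate the treatment effect", with a two-sided 95% interval. The medians come from Kaplan-Meier curves. For deaths, the SAP says: "The table and figures should impute values of 28 days for patients who died". The protocol says: "In these curves, deaths will be counted as being in the hospital at day 28".

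**What is absent.** Neither document says how the interval for the median difference is to be computed, and neither names an effect measure on the rank scale. The Cox model in SAP section 11 is a sensitivity analysis, run only when a baseline characteristic is imbalanced at p<.05.

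**The concern.** The test and the estimate answer different questions. The test compares whole distributions and places a death on day 5 below a patient still in hospital on day 28. In the median calculation those two patients have the same value, and only the middle of each distribution counts.

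Two things follow. First, the median difference carries less information than the rank sum, so its interval can cover 0 when the test is significant. Second, if the arms differed mainly in deaths, the test would respond more than the reported effect would. In both cases the report would hold a significant p-value with no effect size and interval for the quantity that was tested. Any such measure chosen later would be chosen with the results in view. The same analysis is planned for the age, formulation and virology subgroups, where smaller numbers make medians less precise still.

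**Working it through.** **Inputs.** Protocol 9.2 and Table 9, 1.25-day row: log-days mean 1.83 (SD .66) on placebo and 1.58 (SD .76) on treatment, N = 258, 80% power, 290 recruited. Allocation is 1:1. The documents give no mortality rate and no interval method; I assumed 0%, 5% or 10% deaths per arm, uniform over 28 days, no loss to follow-up, and bootstrap intervals.

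**1. The plan's own figure.** Per arm, n = (1.960 + 0.842)² × (.66² + .76²) / .25² = 7.85 × 1.0132 / 0.0625 ≈ 127.3, so 128 per arm (256 in total). The unequal-variance t-test gives 129 per arm, which is the stated 258, with power 80.2%. All six N in Table 9 reproduce from the printed moments.

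**2. Precision of the median difference, 129 per arm, no deaths.**
- Medians: exp(1.83) = 6.23 and exp(1.58) = 4.85 days; difference 1.38 days.
- The SE of a log-normal sample median is 1.2533 × SD × median / √n, which gives 0.454 and 0.407. The SE of the difference is √(0.454² + 0.407²) = 0.61.
- z = 1.38 / 0.61 = 2.26. The chance that the 95% interval excludes 0 is Φ(2.26 − 1.96) ≈ 62%.
- For 80%: 258 × (2.80 / 2.26)² ≈ 396 patients. Moments taken unrounded from mean 7.7 and variance 33.2 give about 410, against 266 for the planned calculation on the same footing.

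**3. Simulation.** Log-normal stays are cut at 28 days. The rank test puts deaths worst and uses its asymptotic p-value in place of the permutation one. The median difference sets deaths to 28 days.

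| Scenario | Of trials with p<.05, share whose median interval includes 0 |
|---|---|
| 1.25 days, 129 per arm, no deaths | 22–26% |
| 1.25 days, 145 per arm, no deaths | 22–23% |
| 1.25 days, 145 per arm, 5% or 10% deaths in both arms | 27% |
| 1.5 days, 145 per arm, no deaths | 14–15% |
| 1.0 day, 145 per arm, no deaths | 32–33% |

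Ranges come from repeated runs. At 129 per arm the rank test was significant in 77–79% of trials and the median interval excluded 0 in 58–61%; the mismatch was 18–20% of all trials. A normal-theory interval with a bootstrap SE gave 25–29% of significant trials at the 1.25-day effect. Among significant trials the median difference had the opposite sign in 0.2% or fewer.

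**4. A difference in deaths only (illustration, assumed rates).** With identical stays, 145 per arm, and 10% against 2% deaths, the rank test was significant in 21% of trials and the median interval excluded 0 in 9%. In 60% of the significant trials the median interval included 0.

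**5. The matching estimate.** With larger ranks worse, as in Appendix 1, let W be the NTZ rank sum and n₁, n₀ the arm sizes. The probability that an NTZ patient ranks better, ties one half, is 1 − [W − n₁(n₁+1)/2] / (n₁n₀), a linear function of the test statistic. At the design effect without deaths it is Φ(.25 / √(.66² + .76²)) = Φ(0.248) = 0.598. In simulation its 95% interval, here from an analytic SE, was about ±0.07 and included 0.5 in none of the significant trials.

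**The case against.** The strongest reply is that an interval covering 0 beside a significant p-value is not a conflict. In these trials the median difference nearly always favours the same arm as the test; it is simply less precise. The mismatch also gathers in borderline results: in one run at 129 per arm it was about 11% of trials with p<.01 and about 53% of those with p between .01 and .05. This stands. A reader might infer that estimate and test would point in opposite directions, or that the primary conclusion is unsafe. The documents support neither reading: the decision rests on the permutation test alone, and its error rate does not depend on the median.

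The SAP also presents its Kaplan-Meier table and figure as descriptive, tabulates the quartiles, analyses mortality separately with a hazard ratio and interval, and counts deaths as hospitalized in the day-by-day proportions. So deaths are not hidden, and equal death rates changed the result little. This softens the point. But both documents still name the median difference as the estimate of the treatment effect, and none of the other analyses gives an effect size for the ranked outcome.

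Finally, the protocol frames its target in days because days are easy to interpret, and 0.60 cannot be read against 1.25 days. That is a sound reason to keep the median. Replacing it would be a preference that the documents do not call for.

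**Conclusion.** The gap is real and modest. Test and estimate are different quantities that treat deaths differently, and no estimate with an interval matches the test. At the 1.25-day effect with 258 to 290 patients, roughly 22% to 27% of significant trials would carry a median interval that includes 0. With 290 patients the share runs from about 14% at 1.5 days to 33% at 1.0 day.

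These figures are conditional. They rest on the protocol's log-normal model, an assumed bootstrap interval, assumed deaths of 0% to 10% equal in both arms, and no withdrawals. One in four should therefore not be read as a general property of the trial. The type I error, the sample size and the primary decision are untouched. This is a worthwhile improvement in reporting, not a flaw in the test.

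**What to change.** In SAP section 11, before unblinding:

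1. Keep the difference in medians with its 95% interval as the clinically readable summary, and name the interval method.
2. Add beside it the probability that an NTZ patient ranks better than a placebo patient, ties one half, with a 95% interval from a bootstrap that resamples patients within arm and re-ranks each time.
3. State that it uses the same Shaw-Fay ranks as the test, including the ranks that the promised R code assigns to patients lost to follow-up. With withdrawals, the rule for ties alone does not define the quantity.

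Do not obtain the interval by inverting the permutation test. That needs an assumed family of alternatives, such as a shift, which the plan does not give and which does not suit a ranking of deaths and discharges.

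The cost is a paragraph of SAP text and a few lines of code, with no change to the test, the alpha level, the sample size or data collection. The downside is one more effect measure, on a scale that clinicians know less well.

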### 3. Selected characteristics of participants at baseline (Day 0) (ITT)

Baseline is defined as the last observation prior to study drug administration. P-values using the test of means for continuous variables, test of proportions for binary endpoints or chi-square tests for categorical endpoints

- Demographics [14.1.3]
  - Table: Age (median, 25th and 75th percentile, mean, min, max)
  - Table: number randomized by age group (<2 years, ≥2 years to <8 years, ≥8 years to <13 years, ≥13 years to <18 year, ≥18 years to <65 years, ≥65 years).
  - Sex (%)
  - Self-reported NIH race/ethnicity (%)
  - Medical History (occurring in 5% or more of the study population)
  - BMI for adults age ≥18 years
  - Z score for age <18 years
  - Smoking History
- Baseline Disease Characteristics [14.1.4.1, 14.1.4.2, 14.1.4.3, 14.1.4.4]
  - Influenza vaccination history (categorical - vaccinated the season of enrollment)
  - Confirmed pathogen by multiplex PCR (i.e. Respifinder®). Include totals for pathogen type (e.g. all influenzas), and for each strain (e.g., H1N1 influenza)
  - Days since onset of symptoms (onset of symptoms to randomization).
  - Days since onset of symptoms to first dose.
  - SaO2

- Severity of illness score
  - Sequential Organ Failure Assessment (SOFA) score for subjects  $\geq$  24 months of age
  - Tal bronchiolitis score for subjects  $<$  24 months of age
- Charlson comorbidity index.
- Chronic oxygen use
- Oxygen requirement (yes/no)
- ICU requirement (yes/no)
- Presence of Complications
  - Pneumonia (clinical diagnosis supported by radiographic data)
  - Respiratory failure requiring mechanical ventilation (documentation of mechanical ventilation)
  - ARDS (clinical diagnosis supported by radiographic data)
  - Sepsis (clinical diagnosis)
  - Bronchiolitis (clinical diagnosis)
- Presence of symptoms for each of the following (defined as 2 or 3 = symptoms present):
  - Cough
  - Sore throat
  - Fatigue
  - Headache
  - Myalgia
  - Rhinorrhea
  - Nausea
  - Vomiting
  - Diarrhea
- CBC with differential white cell count (to include neutrophil, lymphocyte, and eosinophil percentages), hemoglobin, hematocrit, and platelets
- Blood chemistries (creatinine, ALT/GPT, AST/GOT, total bilirubin, LDH, CRP)
- Global Assessment
  - Adult
    - Overall question
    - Function question
  - Pediatric
    - Activity
    - Diet

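### The only covariate-adjusted (supportive) analysis of the primary endpoint takes its covariates from baseline p < .05, so chance picks them; name them in advance instead

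*SAP*

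**What the plan says.** SAP Section 3 lists the baseline characteristics and calls for between-arm tests on them: "P-values using the test of means for continuous variables, test of proportions for binary endpoints or chi-square tests for categorical endpoints". The list covers demographics, disease characteristics, complications, symptoms, blood counts, chemistries and the global assessment questions. Two entries are open-ended: "Medical History (occurring in 5% or more of the study population") and, for pathogens, "Include totals for pathogen type (e.g. all influenzas), and for each strain (e.g., H1N1 influenza"). Measures that could plausibly predict length of stay are on the same list. They include age, SaO2, oxygen and ICU requirement, days since onset, the "Charlson comorbidity index", and the severity scores ("Sequential Organ Failure Assessment (SOFA) score for subjects" aged 24 months or more, Tal score below that age).

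SAP Section 11 then calls for a Cox model "For any imbalance seen in baseline characteristics" at p < .05. Deaths get an event time of 28 days, and missing discharge dates are censored at last follow-up. The instruction is the last bullet of a list introduced as "Sensitivity analyzes to exam effect of missing death or discharge data". It does not say outright that the flagged variables become the Cox covariates, or whether there is one joint model or one per variable. Adjusting for the flagged variables is the only reading that gives the rule a purpose.

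The primary test (Protocol Section 9.1, SAP Appendix 1) is an unadjusted Shaw-Fay rank permutation test at two-sided .05. The effect estimate is an unadjusted difference in Kaplan-Meier medians. Neither document names a covariate for any analysis of the primary endpoint, and the stratification factors (site and age under 12, Protocol Section 5.1) appear in neither the primary test nor the Cox model.

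**The concern.** In a randomised trial a baseline p-value below .05 is a chance event. It carries no information on whether the variable predicts hospital stay. The rule could adjust for eosinophil percentage at p = .04 and leave out SaO2 at p = .10. It would also leave out a strongly prognostic variable that happened to be balanced, although adjusting for that variable would still sharpen the comparison.

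Two things are at stake. The adjusted result cannot be specified before the arm-level data are seen, so it is weak support for the primary result. And the adjusted analysis gives up most of the precision that is the main reason to adjust.

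**Working it through.** **1. The plan's own sample size.** Inputs from Protocol Section 9.2, Table 9, 1.25-day row: log-scale means 1.83 and 1.58, SDs .66 and .76, two-sided .05, 1:1 allocation, Satterthwaite t-test. With 129 per arm:

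- SE = sqrt((.66² + .76²)/129) = sqrt(1.0132/129) = .0886
- noncentrality = (1.83 − 1.58)/.0886 = 2.82
- power = 80%, so N = 258 is reproduced. The other five rows of Table 9 also match.

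With unrounded moments (1.819/.667 against 1.571/.766), power at N = 258 is 79%.

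**2. Number of baseline tests.** Named items in SAP Section 3: 7 demographic (before medical history) + 11 disease characteristics (pathogen counted once) + 5 complications + 9 symptoms + 7 blood count + 6 chemistry + 4 global assessment = 49. Medical-history items and pathogen-level tests add to this. About 50 to 60 is a modest reading; testing every pathogen would give 70 or more.

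**3. Chance imbalances.** For k tests at .05, the expected number is .05k. If tests are independent, P(at least one) = 1 − .95^k.

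| k | Expected | P(at least one), independent |
|---|---|---|
| 49 | 2.45 | 92% |
| 55 | 2.75 | 94% |
| 60 | 3.00 | 95% |

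Many items are correlated. Simulating 55 equicorrelated tests (100,000 draws) gives P(at least one) of 92%, 83% and 64% at correlations of .1, .3 and .5. The expected number stays near 2.75.

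**4. Whether a prognostic variable gets in.** Each enters with probability about .05. If there are 5 independent ones, none enters in .95^5 = 77% of trials; if 7, .95^7 = 70%.

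**5. Precision available from pre-specified covariates.** Multiply both SDs by sqrt(1 − R²), where R² is the share of the variance of log stay explained by baseline covariates. The noncentrality becomes 2.82/sqrt(1 − R²). The documents give no R², so these values are assumptions.

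| Assumed R² | Power, printed moments | Power, unrounded moments |
|---|---|---|
| 0 | 80% | 79% |
| .05 | 82% | 81% |
| .10 | 84% | 83% |
| .20 | 88% | 87% |
| .30 | 92% | 91% |

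**6. What the triggered rule recovers.** Simulation with N = 258, log-scale effect .25, common SD .71, five independent prognostic covariates, linear regression on log days and 10,000 runs per setting:

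| Assumed R² | Unadjusted | Adjusted only where baseline p < .05 | All five, pre-specified |
|---|---|---|---|
| .10 | 80.2% | 80.4% | 83.5% |
| .20 | 79.9% | 80.8% | 87.8% |
| .30 | 80.9% | 82.0% | 91.8% |

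The triggered rule gains about 0.2 to 1 percentage point over no adjustment; pre-specification gains about 3 to 11. With no treatment effect, the triggered rule rejected in 4.1% to 4.7% of runs, so it showed no inflation of type I error.

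**The case against.** The strongest reply is that this is one supportive bullet. A reader might infer that the primary result depends on chance imbalances or that its type I error is at risk. The documents do not support that: Protocol Section 9.1 and SAP Appendix 1 fix the ranking, the permutation and the alpha level, and no baseline p-value can alter them. This part of the reply stands in full.

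A reader might also take the 82% to 92% as power the trial would gain. It is not. With the unadjusted test remaining primary, the trial keeps its planned 80%, and the gain belongs to the adjusted analysis alone. The figures come from a t-test on log days without deaths or censoring, not from adjusted Shaw-Fay ranks.

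Three further cautions stand:

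- It would be too strong to say that known predictors of stay go unused. Neither document reports how any baseline variable relates to length of stay, and the plausible ones are on the screened list and could enter by chance. The accurate statement is that none is pre-specified.
- SAP Section 3 tabulates oxygen and ICU requirement as baseline. But the screening and baseline procedures (Protocol Sections 6.2.1 and 6.2.3.1) list chronic oxygen use and SaO2, not acute oxygen requirement or ICU status. Oxygen use and ICU dates are abstracted around discharge (Section 6.2.8). Their pre-dose status needs confirming.
- The 92% to 95% figure assumes independent tests, so the range down to 64% is the fair statement. Stratification at age 12 also partly balances age, so 5% is not exact for that variable.

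None of this defends choosing covariates by baseline significance.

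**Conclusion.** The point holds for the supportive adjusted analysis, and the plan should be changed there. On about 50 to 60 tests, 2.5 to 3 chance imbalances are expected, with at least one in roughly 64% to 95% of trials. The lower end assumes a common correlation of .5 between tests; the upper end assumes independence. The count depends on how pathogens and medical history are tabulated, which the SAP leaves open. The triggered rule recovers almost none of the precision that a fixed covariate list could give. How large that precision is depends on an R² that the documents do not supply.

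A smaller, separate point concerns the baseline symptom table in SAP Section 3. It has nine symptoms and omits difficulty breathing, which the protocol diary scores (Section 7.3.1.2). The screen is not blind to respiratory status, because SaO2, oxygen requirement and SOFA are on the list.

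**What to change.** Delete the p < .05 trigger from SAP Section 11. Before unblinding, pre-specify one adjusted analysis of the primary endpoint, to be run whatever the baseline table shows. State that it is supportive and that the unadjusted Shaw-Fay test remains primary and decides if the two disagree.

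One workable form keeps the planned method:

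1. Compute the Shaw-Fay ranks as in SAP Appendix 1.
2. Blind to arm, regress the ranks on the stratification factors (site, age under 12) and a short list from SAP Section 3: age, SOFA or Tal score, SaO2, Charlson index and days from onset to randomisation. Add oxygen and ICU requirement if they are confirmed as pre-dose values.
3. State a simple rule for missing covariates, also applied blind to arm.
4. Apply the permutation test to the residuals.

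Once the trigger is gone, the baseline p-values serve no analysis, and whether to keep them is a matter of presentation. Add difficulty breathing to the baseline symptom table.

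The cost is SAP wording and a few lines of code, with no new data collection beyond confirming when oxygen and ICU status were recorded. The one real downside is that a single covariate list must be agreed and then kept.

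### Minor: read literally, the SAP's conditional Cox sensitivity model scores a death better than still being in hospital at Day 28

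*SAP*

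**What the plan says.** The last sensitivity bullet of SAP section 11 begins "For any imbalance seen in baseline characteristics", sets the threshold at p below .05, and tells the analyst to "perform a cox proportional hazards model with deaths receiving event times of 28 days". It censors missing discharge dates at last follow-up. It does not mention patients who are alive and still in hospital at Day 28.

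Two places supply the rule for those patients. Protocol 9.1: "The primary endpoint will be time to hospital discharge, censored at 28 days". SAP Appendix 1: "Observations will be censored at 28 days if discharge or death does not occur before 28 days".

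Three places say how a death should count:

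- Protocol 9.1, primary analysis: "Patients who die by Day 28 will receive the worst ranks, (i.e., worse than any patients who remain hospitalized".
- SAP Appendix 1: "Patients who die will be given worse ranks than those who are alive". In its Table 1, where larger ranks are worse, the three deaths rank 6 to 8 and the living inpatient ranks 5.
- Protocol 9.2, on the Kaplan-Meier curves: "In these curves, deaths will be counted as being in the hospital at day 28".

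**The concern.** For a hazard of discharge, an event is the good outcome and censoring at the end of follow-up is the bad one. If a death is an event at Day 28 and a living inpatient is censored at Day 28, the model credits the death with a discharge that the inpatient never gets. The primary ranking orders these two patients the other way, and the protocol's rule for the curves treats a death as not discharged.

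This is the only covariate-adjusted analysis of the primary endpoint in the SAP, and it is used only when a baseline imbalance has raised doubt about the unadjusted result. A mortality difference could then be muted in the adjusted HR, in either direction. If one arm has deaths where the other has long stays, the HR could lean toward the arm with more deaths.

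**Working it through.** The documents give no figure for this model to reproduce, so the check is on the direction and size of the effect of the coding. HR above 1 means faster discharge on nitazoxanide (NTZ).

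**1. Direction, on the SAP's own example.** Take the eight patients of SAP Appendix 1, Table 1. Persons 1 to 3 die (person 3 after discharge, but ranked as a death), person 4 is in hospital at Day 28, and the others are discharged on Days 15, 5, 2 and 2. Under no treatment effect, each patient's Cox score contribution is δ − H(t), where H is the sum of events over number at risk.

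- Deaths as events at 28: H(28) = 2/8 + 1/6 + 1/5 + 3/4 = 1.367. Each death scores 1 − 1.367 = −0.367. The inpatient scores 0 − 1.367 = −1.367.
- Deaths censored at 28: H(28) = 2/8 + 1/6 + 1/5 = 0.617. All four score −0.617.

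As written, death is better than being in hospital by one full event. With censoring the two tie.

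**2. Inputs for size.** N is 290 at 1:1 (protocol 3.4), so 145 per arm. Hospital days have mean 7.7 and variance 33.2 (protocol 9.2). The protocol's formulas give v = ln(1 + 33.2/7.7²) = 0.445, √v = 0.667 and m = ln 7.7 − 0.445/2 = 1.819. The protocol's table prints .66 and 1.83, a difference that does not matter here. Stays are log-normal, truncated at 28 days. Death rates are assumptions. The share in hospital at Day 28 is set at 4%, from the roughly 4% of observational data that protocol 9.2 removed by truncation at 28 days. That is a proxy and may include deaths, so other values are shown.

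**3. Constructed arms.** Give both arms identical discharge times, then put 10 deaths on NTZ against 10 living inpatients on placebo. The HR as written is 1.10 (95% CI 0.87 to 1.39, Efron) or 1.07 (Breslow). With deaths censored it is 1.00. For 5 to 15 such patients the range as written is 1.05 to 1.16 (Efron) or 1.04 to 1.12 (Breslow). With 7 deaths and 4 inpatients in each arm, the HR is 1.00 under either coding.

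**4. Simulated trials** (2000 per scenario, same stay in survivors). Shift = (ln HR as written − ln HR with deaths censored) / SE, with SE about 0.12. For example, ln(0.903/0.869) = 0.038, and 0.038/0.12 is about 0.3.

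| Deaths, NTZ vs placebo | In hospital at Day 28 | HR as written, Efron / Breslow | HR, deaths censored | Shift in SE |
|---|---|---|---|---|
| 2% vs 1% | 4% each | 0.976 / 0.975 | 0.968 | 0.07 / 0.06 |
| 6% vs 3% | 4% each | 0.938 / 0.932 | 0.915 | 0.19 / 0.15 |
| 10% vs 5% | 4% each | 0.903 / 0.894 | 0.869 | 0.31 / 0.22 |
| 5% vs 10% | 4% each | 1.108 / 1.120 | 1.152 | about −0.3 / −0.2 |
| 5% vs 5% | 4% each | 1.000 / 1.001 | 1.001 | about 0 |
| 10% vs 5% | none | 0.870 / 0.870 | 0.862 | 0.08 |
| 6% vs 3% | 2% vs 5% | 1.048 / 1.034 | 1.003 | about 0.36 / 0.25 |
| 10% vs 5% | 2% vs 7% | 1.079 / 1.049 | 0.995 | 0.64 / 0.42 |

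With equal inpatient shares the HR moves toward 1. In the last two rows, where excess deaths replace long stays, it moves away from 1 and favours the arm with more deaths.

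**The case against.** **Wording.** The bullet may use an event time loosely, meaning only that 28 is entered as the time, much as the SAP's descriptive table does for deaths. That is possible. But a neighbouring bullet has missing dates "imputed in the placebo group as censored at the time of last follow up and in the experimental group are imputed as events at day" (the day meant is Day 28), so the section does separate an event from a censored time. If only a time value was meant, the status still has to be stated, because the status decides the result.

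**Silence on inpatients.** A reader might infer that the Cox bullet itself censors living inpatients at Day 28. It does not; the rule comes from protocol 9.1 and SAP Appendix 1. If their later discharge times were used instead, a death at Day 28 would still count as the better outcome.

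**Composite label.** Section 11 titles its curve discharge/death, and Appendix 1 names both outcomes in the endpoint. Under that label, coding death as an event is consistent. The order of a death and a living inpatient remains reversed.

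**Stakes.** The model is a sensitivity analysis that runs only after a baseline imbalance. This stands, and is why the point is minor.

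**Remedy.** Censoring deaths at Day 28 ties them with living inpatients and does not rank them worse. This also stands. It matches the protocol's rule for the curves, while the ranking of death as worst stays with the Shaw-Fay test.

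**Conclusion.** Taken literally, the Cox bullet is wrong: combined with censoring of living inpatients at Day 28, it scores a death above continued hospitalisation, against protocol 9.1, SAP Appendix 1 and protocol 9.2. With 4% inpatients in each arm and the same stay in survivors, the shift is about 0.06 to 0.31 SE at death rates from 2% vs 1% up to 10% vs 5%. With no inpatients it is 0.08 SE at 10% vs 5%. When excess deaths replace long stays it reaches about 0.6 SE (Efron) or 0.4 SE (Breslow) in the case examined. All of this rests on assumed death and inpatient rates.

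Three stronger readings are not supported:

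- That the coding always pulls the HR toward 1 by at most about 0.3 SE. This holds only with equal inpatient shares and the same stay in survivors.
- That the trial's main result is compromised. The Shaw-Fay p-value does not use this coding, and SAP section 7 analyses mortality separately.
- That the p<.05 trigger can never pick up a randomisation factor. Site is not on the baseline list in SAP section 3 and the age bands cut at 13 rather than 12, but age is also tested there as a continuous variable. The trigger is a design choice, not an error.

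**What to change.** In the Cox bullet, state that the event is discharge, and that patients who die by Day 28 stay in the risk set and are censored at Day 28 as not discharged, as are patients alive and in hospital at Day 28. This costs a few lines of SAP wording and a small change in code. It needs no new data and leaves the primary p-value unchanged.

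Optional and separate: fit one Cox model stratified by the randomisation factors of protocol 5.1 (site, and age under 12 or 12 and over) whether or not the p<.05 trigger is met. If the strata are not prognostic, up to 16 of them (8 sites × 2 age groups) raised the SE of the log HR from 0.123 to 0.129 in simulation, assuming 18% children and 9% not discharged by Day 28. The coding fix does not depend on this change.
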